9.6.1. Case Report Forms (CRFs)/Data Collection Tools (DCTs)/Electronic Data Record

As used in this protocol, the term DCT should be understood to refer to either a paper form or an electronic data record or both, depending on the data collection method used in this study.

A DCT is required and should be completed for the record of each curated patient. The completed original DCTs should not be made available in any form to third parties. Concerto HealthAI shall ensure that its DCTs are securely stored in encrypted electronic and/or paper form and will be password protected or secured in a locked room to prevent access by unauthorized third parties.

Concerto HealthAI has ultimate responsibility for the collection and reporting of curated data required for the study entered on the DCTs and any other data collection forms and ensuring that they meet the data curation specifications provided by Pfizer. Any corrections to entries made in the DCTs or source documents must be fully captured in an audit trail.

9.6.2. Record Retention

Unless expressly agreed to via a separate written agreement by Concerto HealthAI and Pfizer, Concerto HealthAI will retain all study-related documents, including copies of all DCTs, safety reporting forms, source documents utilized for curation services, and adequate documentation of relevant correspondence (eg, letters, meeting minutes, and telephone call reports), for the periods specified in this [Section 9.6.2](#) or as required by applicable law, whichever is longer, unless Pfizer authorizes, in writing, earlier destruction. Complete and accurate accounting records relating to the services Concerto HealthAI provides for this study will be maintained in accordance with generally accepted accounting principles and retained by Concerto HealthAI for at least three (3) years after completion or discontinuation of the study. Other records relating to the services Concerto HealthAI provides relating to this study will be retained for five (5) years. **CCI**

Concerto HealthAI will ensure that it maintains mechanisms to read any records stored in electronic form for at least the minimum retention period for those records specified in this [Section 9.6.2](#).

CCI

If Concerto HealthAI becomes unable for any reason to continue to retain study records for the required period, Pfizer should be prospectively notified. The study records must be transferred to a designee acceptable to Pfizer.

9.7. Data Analysis

Detailed methodology for summary and statistical analyses of data collected in this study will be documented in a SAP, which will be dated, filed and maintained by the sponsor. The SAP may modify the plans outlined in the protocol; any major modifications of primary endpoint definitions or their analyses would be reflected in a protocol amendment.

9.8. Quality Control

All data abstracted from the Definitive Oncology Dataset by CRNs will undergo an independent quality control review, with evaluation for consistency, completeness, and outlier values. This review is conducted by a supervising Curation Manager at Concerto HealthAI and through programmatic evaluation of study data. Data queries generated as part of quality review are documented and resolved, with documentation of queries and resolution maintained in a complete query log.

Data housed in electronic case report forms will then be exported to SAS datasets for data cleaning and preparation, creation of derived values, and preparation of analysis datasets. Data will then undergo initial statistical review, including examination of all fields for outlier values, and evaluation for internal consistency of study data. Values that are flagged as potentially anomalous during statistical review will be queried and resolved before analysis datasets are finalized. All study data also undergoes scientific review of study results prior to data lock.

9.9. Limitations of the Research Methods

This study reflects treatment practice patterns only within the U.S. who are part of the Definitive Oncology Dataset. The majority of the data reflects treatment in community oncology settings (80%). It is possible that treatment patterns may differ in academic centers compared with community settings.

This study is retrospective. With the advent of newer therapies in breast cancer, it is expected that treatment patterns will change during the next few years, and therefore, this study may not be reflective of future breast cancer treatment patterns.

It is possible that patients within the Definitive Oncology Dataset differ from the underlying breast cancer population in ways that may not be measurable; therefore, study results may not be generalizable to other settings.

Some measurements may not be consistently available from patient records in the Definitive Oncology Dataset.

9.10. Other Aspects

Not applicable.

10. PROTECTION OF HUMAN SUBJECTS

10.1. Patient Information

Concerto HealthAI and Pfizer may provide the other party with access to certain information that can be used by itself or in combination with other available information to identify a specific individual included in the study (“patient personal data”) so long as prior written approval of the party receiving the materials is obtained. For sake of clarity, key-coded data relating to individual persons is considered to be personal data. Neither Concerto HealthAI nor Pfizer will attempt to re-identify study subjects. Both parties will implement appropriate internal measures to minimize the risk of any re-identification of study subjects.

All parties will comply with all applicable laws, including laws regarding the implementation of organizational and technical measures to ensure protection of patient personal data, and in accordance with the Pfizer/Concerto HealthAI Collaboration Agreement. Such measures will include omitting patient names or other directly identifiable data in any reports, publications, or other disclosures, except where required by applicable laws or where there is valid written consent or authorization on file.

[figure not shown]
The party sharing patient personal data or samples is responsible for providing and obtaining any legally-required notice and consent from individuals, or for arranging for the study investigator and site to obtain such notice and consent from individuals, with respect to such patient personal data or samples for the purposes contemplated by this Protocol.

In case of data transfer, processing and use, both Concerto HealthAI and Pfizer will maintain high standards of confidentiality and protection of patients’ personal data consistent with applicable privacy laws.

Neither Concerto HealthAI nor Pfizer will transfer, or permit any third party to transfer personal data provided by the other party across any national borders without prior written consent of the party providing such data, unless specifically authorized to do so. In the event any such cross-border transfer is authorized, the party transferring such personal data across national borders is responsible for ensuring that any transfer of personal data across national borders (whether performed by itself or a third party) complies with all applicable laws.

Concerto HealthAI and Pfizer will ensure that any patient personal data is not processed in a way that is incompatible with the purposes for which it was collected or subsequently authorized by the individual from whom it was obtained. For the sake of clarity, the process of de-identification does not render the data incompatible for the purposes for which it was collected for this study.

PFIZER CONFIDENTIAL

Concerto HealthAI and Pfizer will apply adequate and commercially reasonable electronic, physical, and other safeguards appropriate to the nature of the information to prevent any accidental, unauthorized or unlawful use, access, alteration, loss or disclosure of personal data.

10.2. Patient Consent

As this study does not involve data subject to privacy laws according to applicable legal requirements, obtaining informed consent from patients by Pfizer is not required.

10.3. Institutional Review Board (IRB)/Independent Ethics Committee (IEC)

There must be prospective approval of the study protocol, protocol amendments, and other relevant documents (eg, informed consent forms if applicable) from the relevant IRBs/IECs. All correspondence with the IRB/IEC must be retained. Copies of IRB/IEC approvals must be forwarded to Pfizer.

10.4. Ethical Conduct of the Study

The study will be conducted in accordance with legal and regulatory requirements, as well as with scientific purpose, value and rigor and follow generally accepted research practices described in Good Practices for Outcomes Research issued by the International Society for Pharmacoeconomics and Outcomes Research (ISPOR).

11. MANAGEMENT AND REPORTING OF ADVERSE EVENTS/ADVERSE REACTIONS

11.1. Structured Data Analysis

[figure not shown]
This study involves data that exist as structured data by the time of study start or a combination of existing structured data and unstructured data, which will be converted to structured form during the implementation of the protocol solely by a computer using automated/algorithmic methods, such as natural language processing.

In these data sources, individual patient data are not retrieved or validated, and it is not possible to link (ie, identify a potential association between) a particular product and medical event for any individual. Thus, the minimum criteria for reporting an adverse event (AE) (ie, identifiable patient, identifiable reporter, a suspect product, and event) cannot be met.

11.2. Human Review of Unstructured Data

This study protocol requires human review of patient-level unstructured data; unstructured data refer to verbatim medical data, including text-based descriptions and visual depictions of medical information, such as medical records, images of physician notes, neurological scans, X-rays, or narrative fields in a database. The reviewer is obligated to report adverse events (AEs) with explicit attribution to any Pfizer drug that appear in the reviewed information (defined per the patient population and study period specified in the protocol). Explicit

PFIZER CONFIDENTIAL

attribution is not inferred by a temporal relationship between drug administration and an AE, but must be based on a definite statement of causality by a healthcare provider linking drug administration to the AE.

The requirements for reporting safety events on the non-interventional study (NIS) adverse event monitoring (AEM) Report Form to Pfizer Safety are as follows:

- All serious and non-serious AEs with explicit attribution to **any Pfizer drug** that appear in the reviewed information must be recorded on the NIS AEM Report Form and reported, within 24 hours of awareness, to Pfizer Safety using the NIS AEM Report Form.
- Scenarios involving drug exposure, including exposure during pregnancy, exposure during breast feeding, medication error, overdose, misuse, extravasation, lack of efficacy, and occupational exposure associated with the use of a Pfizer product must be reported, within 24 hours of awareness, to Pfizer Safety using the NIS AEM Report Form.

For these AEs with an explicit attribution or scenarios involving exposure to a Pfizer product, the safety information identified in the unstructured data reviewed is captured in the Event Narrative section of the report form, and constitutes all clinical information known regarding these AEs. No follow-up on related AEs will be conducted.

[figure not shown]
All the demographic fields on the NIS AEM Report Form may not necessarily be completed, as the form designates, since not all elements will be available due to privacy concerns with the use of secondary data sources. While not all demographic fields will be completed, at the very least, at least one patient identifier (eg, gender, age as captured in the narrative field of the form) will be reported on the NIS AEM Report Form, thus allowing the report to be considered a valid one in accordance with pharmacovigilance legislation. All identifiers will be limited to generalities, such as the statement “A 35-year-old female...” or “An elderly male...” Other identifiers will have been removed.

Additionally, the onset/start dates and stop dates for “Illness”, “Study Drug”, and “Drug Name” may be documented in month/year (mmm/yyyy) format rather than identifying the actual date of occurrence within the month /year of occurrence in the day/month/year (DD/MMM/YYYY) format.

CCI

PFIZER CONFIDENTIAL

CCI

12. PLANS FOR DISSEMINATING AND COMMUNICATING STUDY RESULTS

CCI

In the event of any prohibition or restriction imposed (eg, clinical hold) by an applicable competent authority in any area of the world, or if Concerto HealthAI is aware of any new information which might influence the evaluation of the benefits and risks of a Pfizer product, Pfizer should be informed immediately.

14. LIST OF TABLES

None.

15. LIST OF FIGURES

None.

ANNEX 1. LIST OF STAND ALONE DOCUMENTS

None.

ANNEX 2. ENCEPP CHECKLIST FOR STUDY PROTOCOLS

Not applicable.

ANNEX 3. ADDITIONAL INFORMATION

Not applicable.

1. AMENDMENTS FROM PREVIOUS VERSION(S)

Not applicable (first version).

2. INTRODUCTION

Note: in this document any text taken directly from the non-interventional (NI) study protocol is *italicised*.

The treatment landscape for HR+/HER2- advanced and metastatic breast cancer (A/MBC) has changed as multiple CDK4/6i drugs in combination with aromatase inhibitor (AI) are approved for use in the first line and subsequent lines of therapy. The present study is designed to describe treatment patterns and clinical outcomes in patients diagnosed with HR+/HER2- A/MBC who received CDK 4/6i combination therapy with AI as initial endocrine-based treatment in the U.S. community oncology setting.

2.1. Study Design

This is an observational, retrospective study involving medical chart review. Eligible patients will be identified and accrued from the Concerto HealthAI Definitive Oncology Dataset. All study data are secondary data and will have been collected retrospectively from existing clinical data originally collected as part of routine care.

2.1.1. Study Population

The study will include adult patients 18 years or older, diagnosed with HR+/HER2- A/MBC who initiated CDK4/6i combination therapy with AI as the initial endocrine-based therapy on or after 2/3/2015 and before 4/1/2019.

[figure not shown]
2.1.2. Data Source

Concerto HealthAI maintains a network of community oncology practices representing a geographically and demographically diverse patient population. Data from these practices have been collected centrally in the Definitive Oncology Dataset, which is the source of data to be collected in this study.

Key features of the Definitive Oncology Dataset include the following.

- *Availability of both structured data (tables, rows and columns) and unstructured data (text and image documents, eg, physician progress notes). The unstructured information is generally not available in other Electronic Medical Record (EMR) data sources, although this is where much of the richest clinical information is found. Together with the structured data, Concerto HealthAI has access to an essentially complete version of the medical oncology health record for each patient. As a result, analysis does not need to rely on proxy measures of key clinical endpoints, as may be the case where only structured EMR data are available.*

PFIZER CONFIDENTIAL

2.1.3. Treatment/Cohort Labels

Patients will be grouped into the following **CCI**

- All Eligible Patients – patients satisfying protocol study inclusion/exclusion criteria and receiving CDK4/6i combination therapy with AI as initial endocrine-based therapy. **CCI**
- Palbociclib + AI Patients – patients receiving Palbociclib with AI as initial endocrine-based therapy.

CCI

2.2. Study Objectives

Primary Objectives:

1. All Eligible Patients:

a. Describe demographic and clinical characteristics.

- *Demographic characteristics will include age, sex, race, insurance status, menopausal status, and region of residence at A/MBC diagnosis.*
- *Clinical characteristics will include stage of initial diagnosis, histology, Eastern Cooperative Oncology Group (ECOG) performance status (where available, Karnofsky performance status will be converted to corresponding ECOG score) and comorbid disease burden, HER2 and Estrogen receptor (ER)/ Progesterone receptor (PR) status, number and sites of distant metastasis at A/MBC diagnosis (if applicable); modalities of treatment received prior to A/MBC diagnosis (chemotherapy, hormone therapy, surgery, radiation therapy) and disease free interval (time between completion of adjuvant therapy and diagnosis of A/MBC).*

b. Describe treatment patterns.

- *Distribution of regimens from the diagnosis of A/MBC through the end of the record.*
- *Sequence of regimens across lines, through the end of the record of systemic therapy.*
- *Description of the dosing employed with administration of palbociclib, ribociclib, and abemaciclib. Description of the dosing will include the starting dose, end dose, dose adjustment (dose increase and dose reduction), reasons for dose adjustment (dose modification, schedule changes, dose delay, hold, or discontinuation), discontinuation, reason, and time to dose adjustment (discontinuation).*

2. *Among patients receiving Palbociclib + AI as initial endocrine-based therapy, examine clinical effectiveness outcomes including:*
 - a. *Real-world progression-free survival (rwPFS) will be assessed for the initial endocrine-based therapy.*
 - b. *Overall survival (OS) will be assessed from start of the initial endocrine-based therapy.*
 - c. *Real-world tumor response (rwTR) will be assessed as best overall response for each regimen received within the initial endocrine-based therapy.*

CCI [REDACTED]

[REDACTED]

[REDACTED]

3. HYPOTHESES AND DECISION RULES

3.1. Statistical Hypotheses

Not applicable.

3.2. Statistical Decision Rules

Not applicable.

3.3. SAMPLE SIZE

The sample size of this study will be based on the actual number of eligible patients available for the study through CRN screening. The study will include all patients (estimated 1100 – 1300 patients) in the data set for the descriptive elements who meet the inclusion/exclusion criteria.

4. ANALYSIS SETS/POPULATIONS

4.1. Full Analysis Set

Includes all patients who satisfy all inclusion and exclusion criteria.

PFIZER CONFIDENTIAL

4.1.1. Inclusion criteria

Patients must meet all of the following inclusion criteria to be eligible for inclusion in the study:

1. *Female or male sex.*
2. *Diagnosis (confirmed by clinical review) of A/MBC, defined as breast cancer at stage IIIB, stage IIIC, stage IV or identified as having distant metastasis.*
3. *Age ≥ 18 years at A/MBC diagnosis.*
4. *Initiated a CDK4/6i in combination with an AI as initial endocrine-based therapy after A/MBC diagnosis on or after 2/3/2015 and before 4/1/2019.*
 - *Note that the date of the start of the inclusion period reflects the month that the first CDK4/6i (ie, Palbociclib) received U.S. FDA approval.*
5. *Evidence of ER or PR positive disease, or absence of any indication of ER and PR negative disease closest to A/MBC diagnosis (ie, patients are eligible without affirmative indication of ER/PR+ status as long as ER/PR- indication is not present).*
6. *Evidence of HER2 negative disease, or absence of any indication of HER2 positive disease closest to A/MBC diagnosis (ie, patients are eligible without affirmative indication of HER2- status as long as HER2+ indication is not present).*

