4.1.2. Exclusion Criteria

Patients meeting any of the following criteria will not be included in the study:

[figure not shown]
Enrollment in an interventional clinical trial for A/MBC during the study observation period.

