5.3. Efficacy/Effectiveness Endpoint(s)

Variable	Operational definition
Real-world progression-free survival	
Time in months from the initial endocrine-based therapy to the first progression or censoring date will be calculated.
 
For the purpose of this study, lines of therapy will be defined as the following Progression-based lines, in which a disease progression must occur for a new regimen to be interpreted as a new line of therapy.
 
Event: Any death or disease progression. Disease progression is taken to have occurred when a pathology report or radiological scan indicates disease progression and/or there is a physician progress note consistent with that determination. If patients did not die or have disease progression, they were censored at their last visit date during the study period for patients with only one line of therapy.

Overall survival	
Time in months from the initial endocrine-based therapy to death due to any cause or censoring date will be calculated.
 
Event: Any death recorded in the data extract. Patients who did not die will be censored at the time of data cutoff (assuming this is the last date the SSDI is searched).

Real-world tumor response	
Real-world tumor response (rwTR) will be assessed as best overall response for each regimen received within the initial endocrine-based therapy.
 
Responses will be classified as Complete response (CR); Partial response (PR); Stable disease (SD); Progressive disease (PD); Not evaluable (NE); or Undocumented. The date of the first positive response (CR or PR) and of the best overall response for each regimen will be collected.

Response rate	
The number of patients with complete response or partial response divided by the number of patients with at least one tumor assessment while on the initial endocrine-based therapy.

PFIZER CONFIDENTIAL

Time to first positive response	Months from the start date of the initial endocrine based therapy to the date of the first positive response (CR or PR).
Duration of response	Month from the date of the first positive response (CR or PR) to the date of first PD assessment or death. Patients without a PD assessment or death are censored at the the data cutoff date.
Duration of initial endocrine-based treatment	Months from the start date of the initial endocrine-based therapy to the end date of the initial endocrine-based therapy.

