7.2. Statistical Analyses

Description of demographic, clinical, and treatment characteristics

Descriptive analyses will be conducted to evaluate the demographic, clinical, and treatment characteristics each of the study cohorts. Results will be reported in aggregate. Categorical variables (eg, ECOG performance status) will be reported as frequency and percentage. Continuous variables such as age will be reported as mean, standard deviation, median, 1st quartile, 3rd quartile, inter-quartile range, minimum, and maximum. In the case of missing observations, the number and percentage of missing values will be reported.

[figure not shown]
Description of effectiveness outcomes

For each of the study cohorts, real-world tumor response and response rate will be reported as frequency and percentage. Real-world progression-free survival, overall survival, time to first positive response, duration of response, duration of initial endocrine-based treatment, duration of all treatment, and Duration of follow-up will be assessed with the Kaplan-Meier method with 95% CIs, and summary tables of the number of events and censored patients. No covariates will be included. All missing values are excluded.

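### OS and rwPFS are ordinary Kaplan-Meier from therapy start, but no readable criterion requires a contributing practice to have been treating the patient then, so time before entry can count as time at risk

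*SAP*

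**What the plan says.** - **Who enters.** The sample comes from an existing records database: "Eligible patients will be identified and accrued from the Concerto HealthAI Definitive Oncology Dataset" (SAP 2.1). The treatment criterion is "Initiated a CDK4/6i in combination with an AI as initial endocrine-based therapy after A/MBC diagnosis on or after 2/3/2015 and before 4/1/2019" (SAP 4.1.1 item 4; the same in Protocol 9.2.1). The only exclusion is "Enrollment in an interventional clinical trial for A/MBC during the study observation period" (SAP 4.1.2), and the Full Analysis Set "Includes all patients who satisfy all inclusion and exclusion criteria" (SAP 4.1).
- **What is collected.** The curated, extracted and derived variables in Protocol 9.3.2 to 9.3.4 include treatments and progression dates from A/MBC diagnosis onward. No date of first visit or first contact with a contributing practice is listed.
- **Time origin.** OS: "Time in months from the initial endocrine-based therapy to death due to any cause or censoring date will be calculated". rwPFS: "Time in months from the initial endocrine-based therapy to the first progression or censoring date will be calculated" (both SAP 5.3).
- **Estimator.** SAP 7.1 specifies unadjusted Kaplan-Meier curves. In SAP 7.2 the time-to-event outcomes "will be assessed with the Kaplan-Meier method with 95% CIs, and summary tables of the number of events and censored patients", without covariates. Neither section mentions an entry time.
- **Completeness of records.** SAP 2.1.2 says that "Concerto HealthAI has access to an essentially complete version of the medical oncology health record for each patient".

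**The concern.** Suppose a patient starts palbociclib + AI at an outside clinic in 2015 and moves to a contributing practice in 2017. The patient meets every readable criterion and is timed from 2015. A similar patient who died at the outside clinic in 2016 never reaches the dataset. Placing the first patient in the risk set from 2015 counts two years in which a death could not have been recorded. This is left truncation. For rwPFS the same holds for progression if the patient arrives still unprogressed on the first regimen.

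OS and rwPFS are Objective 2 results. That objective has no comparator, and SAP 3.1 and 3.2 state no hypotheses or decision rules, so the absolute curves and medians are themselves the findings. A larger sample does not remove this kind of bias. Without a first-visit date, the plan cannot show whether the problem is trivial.

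**Working it through.** **Inputs from the documents.** Protocol 9.5 gives average follow-up as (50/2) + 8 = 33 months. The calendar dates reproduce it: 2/3/2015 to 4/1/2019 is 49.87 months, 4/1/2019 to 12/1/2019 is 8.02 months, and 49.87/2 + 8.02 = 32.95. Potential follow-up is therefore taken as uniform over 8 to 58 months. Protocol 7 supplies benchmarks: OS 38.5 to 60.1 months, median PFS 24.5 months, 12-month survival 95.1% and 12-month progression-free rate 84.1%.

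**Assumptions.** The share f of analysed patients who transfer in on therapy and event-free, and their delay E after therapy start, are not in the documents, so ranges are shown. Event times are exponential with rate λ = ln 2 / median.

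**Median shift.** Beyond E, transfers follow S(t)/S(E) and all others follow S(t). Ordinary Kaplan-Meier therefore estimates S(t) × [(1 − f) + f/S(E)], and the median moves up by ln[(1 − f) + f·exp(λE)]/λ, which is roughly f × E.

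Example for rwPFS with f = 10% and E = 6: λ = 0.6931/24.5 = 0.02829; exp(0.1697) = 1.185; 0.9 + 0.1185 = 1.0185; ln(1.0185)/0.02829 = 0.65 months.

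| True median (months) | 5%, 3 mo | 10%, 6 mo | 20%, 6 mo | 30%, 12 mo |
|---|---|---|---|---|
| rwPFS 24.5 | +0.16 | +0.65 | +1.28 | +4.05 |
| OS 38.5 | +0.15 | +0.63 | +1.25 | +3.88 |
| OS 60.1 | +0.15 | +0.62 | +1.23 | +3.78 |

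**12-month rates, f = 20%, E = 6.**
- Survival: S(6) = √0.951 = 0.9752, and 0.951 × (0.8 + 0.2/0.9752) = 95.6%, against 95.1%.
- Progression-free: S(6) = √0.841 = 0.9171, and 0.841 × (0.8 + 0.2/0.9171) = 85.6%, against 84.1%.

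**Longer delays: entry uniform over 1 to 24 months, f = 10%, median OS 38.5.** True 24-month OS is 2^(−24/38.5) = 64.9%. Among transfers who survive to entry, the mean of 1/S(E) is 23 divided by the integral of S from 1 to 24, that is 23/18.50 = 1.243. The estimate becomes 0.649 × (0.9 + 0.1 × 1.243) = 66.5%, and simulation with the planned censoring also gave 66.5%. At n = 1200 the binomial standard error is √(0.649 × 0.351/1200) = 1.4 points, or about 1.5 once censoring is allowed for. The shift of 1.6 points is about one standard error.

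**Direction and remedy.** An illness-death simulation (true median rwPFS about 24.5; OS median 46.4 in the run without transfers) compared ordinary with delayed-entry Kaplan-Meier at f = 10%, 20% and 30%:
- *On-therapy transfers, entry uniform over 0 to 12 months.* Ordinary rwPFS medians were 25.1, 25.7 and 26.4; delayed entry gave 24.4 to 24.5. Ordinary OS medians were 46.7, 47.0 and 48.1; delayed entry gave 46.5, 46.7 and 47.6, so OS was only partly corrected.
- *Transfers triggered by progression.* Ordinary rwPFS medians were 23.1, 21.8 and 20.5; delayed entry gave 24.4 to 24.6. Ordinary OS medians were 45.2, 43.8 and 42.8; delayed entry gave 44.4, 42.2 and 40.4, further from the truth.

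**Precision for scale.** In the same simulation at N = 1200, the 95% CI for the median was about 4.4 months wide for rwPFS and at least 7.8 for OS, so the half-widths are about 2.2 and 3.9 months.

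**The case against.** The strongest reply concerns size and direction. Nothing in the documents suggests that transfers are common or late. At 10% or less and 6 months or less the median moves by under 0.7 months, well inside the confidence interval. A material shift needs something like 20% to 30% transfers or delays of a year. This stands, and it is why the first request is a count.

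A reader might infer that the bias can only run upward. The documents do not support that. The criteria also admit patients who arrive after progressing, and Protocol 9.3.2 item 19 collects progression dates from A/MBC diagnosis, so such patients can lower both medians.

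A reader might also infer that delayed-entry Kaplan-Meier cures the problem. It does so only if entry time is independent of prognosis, and the simulated OS results show what happens otherwise.

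The comparison with one standard error uses n = 1200, within the 1100 to 1300 estimated for all CDK4/6i + AI patients. Objective 2 concerns palbociclib + AI only. If that cohort is smaller, its standard error is larger and the same shift is less than one standard error.

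The completeness statement in SAP 2.1.2 is not an answer. It describes the content of records already in the dataset and does not say that care began there. Parts of Protocol 9.3.2, 9.5 and 9.6 and of SAP 2.1.3 are redacted, and a rule on records that begin mid-therapy could sit there. The eligibility lists and endpoint definitions are readable and contain none.

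Finally, Protocol 9.9 warns that dataset patients may differ from the wider population. That is a general caution and does not name delayed entry.

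**Conclusion.** The point holds in a limited form. As written, the plan counts pre-entry time as time at risk for anyone who transfers in on therapy. For transfers who are event-free at entry this biases OS and rwPFS upward, by roughly share times delay on the median: from about 0.2 months to about 4 months over shares of 5% to 30% and delays of 3 to 12 months. These figures rest on exponential event times and on shares and delays that the documents do not give. The net effect over all transfers may have either sign. The documents support neither the claim that the reported medians will be materially wrong nor the claim that they will certainly be too favourable. They do show that the plan cannot tell, although one additional date would allow it to. That justifies a change to the analysis of a descriptive study whose absolute curves are the result.

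**What to change.** 1. Add to the Protocol 9.3 variables the date of first visit at a contributing practice. Check it against the start of that practice's electronic records, so that patients already under care are not mistaken for late entrants.
2. Report the number and percentage of patients first seen after therapy start and the distribution of their delay, for All Eligible Patients and for Palbociclib + AI Patients, and how many had progressed before entry.
3. In SAP 7.2, add OS and rwPFS analyses with delayed entry, each patient joining the risk set at the later of therapy start and first visit (SAS 9.4 PROC PHREG accepts an entry time). Patients whose progression precedes entry contribute no risk time to the delayed-entry rwPFS analysis.
4. Repeat OS and rwPFS restricted to patients seen on or before therapy start.
5. State that delayed entry assumes entry time is independent of prognosis, add the issue to the limitations, and interpret the unadjusted curves in light of these analyses.

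The cost is one date to extract and, for some patients, to confirm in the chart, together with SAP wording and extra output. Early risk sets become a little smaller, and the estimates may be slightly less favourable. If late entrants prove few, the count shows it and the unadjusted curves can stand.
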